5.4 Interim Analysis

A formal unblinded interim analysis will be performed to select one of the two active doses for Stage 2 based on primary efficacy endpoint of 2MWD. The interim analysis will be performed when at least 80% of randomised subjects have finished the treatment period of Stage 1. The subjects included in the interim analysis from the data cut are those who have completed the one-year treatment period or who have the 2MWD measurements at the 6-month visit or afterwards. Based on the interim analysis results, the independent DMC will use the prespecified dose selection rule to select one of the Flebogamma 5% DIF doses (2 g/kg or 1 g/kg) to continue the Stage 2 of the clinical trial. Given no safety concern for the Flebogamma[®] 5% DIF doses, the following dose selection rules will be applied:

At the interim analysis, conditional power (the power conditional on the partial information accumulated at the interim analysis) will be calculated for comparisons of Flebogamma[®] 5% DIF 2 g/kg versus Placebo and Flebogamma® 5% DIF 1 g/kg versus Placebo. Between the two active treatment arms, if conditional power based on primary efficacy endpoint of 2MWD in Flebogamma[®] 5% DIF 2 g/kg arm is at least 10% relatively higher than Flebogamma[®] 5% DIF 1 g/kg arm, then choose Flebogamma[®] 5% DIF 2 g/kg to move forward. Otherwise, choose Flebogamma[®] 5% DIF 1 g/kg to move forward in Stage 2.

The conditional power will be calculated for each active treatment arm vs placebo with the randomization ratio 1:1, using the following formula based on the observed data and parameters estimated at the interim analysis (Chang; 2008):

$$CP(Z, \hat{\delta}, s, n_1, n_2) = \Phi\left(\frac{Z\sqrt{\frac{n_1}{2s^2}} - Z_{1-\alpha}\sqrt{\frac{n_1}{2s^2}} + \hat{\delta}(\frac{n_2}{2s^2})}{\sqrt{\frac{n_2}{2s^2}}}\right) = \Phi\left(Z\sqrt{\frac{n_1}{n_2}} - Z_{1-\alpha}\sqrt{\frac{n_1}{n_2}} + \hat{\delta}\sqrt{\frac{n_2}{2s^2}}\right)$$

where Z is the z-test statistics, $\hat{\delta}$ is the estimated mean difference between the treatment arm and placebo, and s is the estimated standard error for the mean of treatment; which are the estimates from the mixed-effect model repeated measures including change from baseline in 2MWD as the dependent variable; treatment, protocol-specified visits, treatment-by-visit interaction, and main part of the body affected (lower extremity versus upper extremity) as the fixed effects; baseline 2MWD measure as a covariate; and measures within-subject at each visit as a repeated measure. n_1 is the number of subjects included in the interim analysis for the treatment arm at Stage 1 and n_2 is the number of subjects planned to be enrolled for treatment arm at Stage 2.

From the last subject first visit of 80% planned randomized subjects in Stage 1 to the final DMC decision of dose selection for Stage 2, subject enrollment will continue for Stage 1. Depending on the study enrollment rate, there could be more than the rest 20% of planned randomized subjects in Stage 1 enrolled (i.e., over-running) or less than the rest of 20% of planned randomized subjects in Stage 1 enrolled (i.e., under-running) when the final DMC dose selection is decided.

For over-running scenario, the over-running subjects will be included in the final analysis for Stage 1 and Stage 2 will enroll the number of subjects as planned. It is not anticipated there will be more than 10% of the planned sample size of Stage 1 for over-running subjects. If over-running subjects exceed 10% of the planned sample size for Stage 1, the study enrollment may be paused until the decision of the final dose selection for Stage 2 by DMC.

For under-running scenario, the enrollment for Stage 1 will be stopped and the remaining subjects not randomized in the Stage 1 will be reallocated to Stage 2 and included in the final analysis for Stage 2. In addition, the number of subjects as planned for Stage 2 will still be enrolled so that the entire study will have the same number of randomized subjects as planned. In this case, there will be more subjects in the selected dose and placebo arms than that as planned.

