10.6 Selection of subjects to be included in the analyses

10.6.1 Population for statistical analysis of efficacy

Two study populations for statistical analysis of efficacy may be used: ITT population and PP population. All efficacy analysis will be primarily run on the ITT population and then they may be run on the PP population.

The **ITT population** will include all randomized subjects. Subjects will be analyzed per the randomized treatment.

The **PP population** will include subjects in the ITT population who have received at least 8 infusions, without having 2 consecutive missed infusions, of any investigational product (test or placebo) during the treatment period, have baseline and at least 1 post-baseline measures of the 2MWD, and have no major protocol violations that might have impact on the primary efficacy assessment (as determined at a data review meeting prior to database lock and unblinding).

The major protocol violations will include, but are not limited to, the following: entry inclusions/exclusions not met, more than 1 consecutive missed infusion or more than 4 missed infusions during the treatment period, randomization error (*i.e.*, wrong treatment received), and treatment unblinded during the study treatment period.

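### The interim dose-selection set leaves out randomised subjects whose last 2MWD is before Month 6, which can bias the choice of dose in either direction

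*SAP*

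**What the plan says.** SAP 5.4 sets the timing: "The interim analysis will be performed when at least 80% of randomised subjects have finished the treatment period of Stage 1". It then restricts the data: the subjects analysed are those who finished the year of treatment "or who have the 2MWD measurements at the 6-month visit or afterwards". Protocol 10.1.4 describes the same interim without this restriction and leaves further detail to the DMC charter, which is not among the documents.

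The quantities that enter conditional power come from a repeated-measures model; the SAP says of them "which are the estimates from the mixed-effect model repeated measures including change from baseline in 2MWD as the dependent variable". In the same formula n1 "is the number of subjects included in the interim analysis for the treatment arm at Stage 1". The 2 g/kg dose goes forward only if its conditional power exceeds that of 1 g/kg by a relative margin of at least 10%; otherwise 1 g/kg goes forward. A proviso that begins "Given no safety concern for the Flebogamma" precedes the rule.

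For efficacy in general, Protocol 10.6.1 says "All efficacy analysis will be primarily run on the ITT population", and ITT means everyone randomised. SAP 10 also puts the final efficacy analyses on ITT.

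**The concern.** Entry to the interim set depends on something that happens after randomisation: still being under observation, with a walk test, at Month 6 or later. Comparisons within such a set are no longer protected by randomisation. The first post-baseline 2MWD is at Week 12, and a likelihood-based MMRM can use a subject who has only that value. The rule discards it.

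The plan is also at odds with itself. Conditional power is meant to predict the final combination test. The Stage 1 p-value in that test comes from an MMRM on all randomised subjects, where Week-12-only subjects contribute. The same people inform the final test but not the choice of dose.

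What is at stake is the dose taken into Stage 2, a choice that cannot be revisited within the trial. Protocol 6.3 lists adverse events, thromboembolic events, haemolysis and repeated missed infusions among the grounds for withdrawal, so early loss that differs by arm is possible. The documents give no rates by arm.

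**Working it through.** **1. The plan's own figures.** SAP 5.3: 33 per arm with 20% dropout gives 33 / (1 - 0.20) = 41.25, rounded up to 42; 3 x 42 = 126 in Stage 1 and 2 x 42 = 84 in Stage 2. These reproduce exactly, and nothing here disputes them.

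**2. Who is affected.** Post-baseline 2MWD in the treatment period is at Weeks 12, 24, 36 and 52 (Protocol 4.5.2.14).

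| 2MWD pattern | Interim set (SAP 5.4) | Final Stage 1 MMRM (ITT) |
|---|---|---|
| No post-baseline value | Out | Contributes no change value |
| Week 12 only, left the trial | Out | Used |
| Left between Weeks 12 and 24, with a discontinuation-visit 2MWD | Unclear: SAP 5.1 remaps that visit to the next scheduled one | Used |
| Missed Week 24, has Week 36 or 52 | In | Used |
| Not yet at Month 6 at the data cut | Out | Used |

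The last group is missing for administrative reasons and is not a source of bias. The second group, and part of the third, is where bias can arise.

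**3. Size, by simulation.** From the documents: 42 per arm, SD 11 m, 1:1:1 allocation, one-sided alpha 0.025, the 10% relative rule. Assumed: both doses truly +4 m; within-subject correlation 0.7; early dropout (after Week 12, before Week 24) of 5% on placebo, 5% on 1 g/kg and 15% on 2 g/kg; later dropout 10%; early leavers have only a Week 12 value. At 42 per arm, 15% is about 6 subjects and 5% about 2. The model was a maximum-likelihood unstructured MMRM without the baseline and body-part covariates, with 1,500 runs per scenario (Monte Carlo error about 1 point). Conditional power was computed with the formula printed in SAP 5.4 and, in brackets, with the standard form, which has n1+n2 where the printed critical-value term has n1. That difference is a separate matter.

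| Early dropouts | 2 g/kg estimate: SAP set / all with any post-baseline 2MWD | P(select 2 g/kg): SAP set | P(select 2 g/kg): all | Shift |
|---|---|---|---|---|
| Walk worse at Week 12 | 4.92 / 3.99 m | 38.5% (47.7%) | 32.5% (39.0%) | +6.0 (+8.7) |
| Unrelated to walking | 3.89 / 3.89 m | 29.3% (36.3%) | 29.9% (36.3%) | -0.6 (0) |
| Walk better at Week 12 | 3.02 / 4.01 m | 23.9% (28.5%) | 31.5% (40.2%) | -7.6 (-11.7) |

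Sensitivity (printed formula):
- Early dropout 5% in every arm: shift of about 1 point or less.
- Early dropout 25% at 2 g/kg: +10.6 (41.1% vs 30.5%), +0.6 (30.1% vs 29.5%) and -12.4 (16.9% vs 29.3%) for worse, unrelated and better.
- Both doses truly +6 m, 15% vs 5%: +2.4 (17.3% vs 14.9%) if worse, -3.6 (11.2% vs 14.8%) if better.
- Correlation 0.5, both doses +4 m, dropouts worse: estimate 4.60 vs 3.93 m, shift +4.3 (34.5% vs 30.2%).

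**4. Plausibility of the bias.** Suppose the dropouts were exactly the worst Week 12 walkers. Removing a lower-tail fraction p raises the remaining mean by phi(z_p)/(1-p) SD: 0.2332/0.85 = 0.2743 for 15% and 0.1031/0.95 = 0.1086 for 5%. Carried to Week 52 with correlation 0.7, the difference from placebo is off by 0.7 x 11 x (0.2743 - 0.1086) = 1.28 m. The simulated 0.9 m lies below this ceiling, as it should.

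**5. Effect through n1.** Take an observed difference of 4 m, s = 11 and n2 = 42. With n1 = 42, Z = 4 / (11 x sqrt(2/42)) = 1.666. The printed formula gives Phi(1.666 - 1.960 + 1.666) = Phi(1.373) = 0.915; the standard form gives 0.713. With n1 = 34 the values are 0.895 and 0.648. Losing subjects therefore lowers that arm's conditional power a little, which partly offsets an upward bias in its estimate.

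**The case against.** Several things limit this point.

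- A reader might infer that anyone without a Week 24 walk test is dropped. The text does not say so: a value at Week 36 or 52, or completing the year, is enough.
- A reader might infer that all early leavers are removed. Under the SAP 5.1 remapping, a subject who leaves between Weeks 12 and 24 and attends the discontinuation visit may count as having a Month 6 value. This narrows the loss but does not remove it. SAP 5.4 does not say whether remapped values count for inclusion, attendance depends on the subject's willingness (Protocol 5.4), and a value remapped to Week 12 would still not qualify.
- The most tempting reading is that the rule favours the less tolerated dose. The documents do not say which dose is less well tolerated, and the direction depends on whether dropouts walk better or worse. Withdrawal for thromboembolism, haemolysis or missed infusions need not track walking at all, and then there is no bias.
- The safety proviso and the default to 1 g/kg are safeguards. They limit the harm but do not correct a biased estimate.
- Simply enlarging the set would create a new problem. The formula treats each included subject as full information, so Week-12-only subjects would raise n1 without matching Week 52 information. This objection stands, and the fix has to deal with it.
- The simulated advantage of using everyone holds because dropout was made to depend on the observed Week 12 value. Dropout driven by unobserved later decline would leave some bias under either rule.

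**Conclusion.** The point holds as a conditional one. The interim set is defined by a post-randomisation event, departs from ITT, and discards Week 12 data that the interim model could use. The dose choice is biased only if early dropout differs by arm and is related to walking, and the sign can go either way. At 15% vs 5% early dropout, true effects of 4 m and correlation 0.7, the 2 g/kg estimate moves by about +0.9 m or -1.0 m, roughly one sixth of the 6 m design effect. The chance of selecting 2 g/kg moves by about +6 to +9 points, about 0, or about -8 to -12 points. These dropout rates, the correlation, the true effects and the strength of the link with walking are assumptions, and the shifts are smaller when both doses truly give 6 m.

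It would be wrong to infer that the final test is invalid. The Stage 1 p-value is specified on ITT and is combined with Stage 2 through a closed test (SAP 10 and 10.1), so type I error is not affected. What suffers is the quality of the dose choice.

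**What to change.** In SAP 5.4, and in the DMC charter if it repeats the rule:

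1. Run the interim MMRM on every randomised Stage 1 subject in the data cut with a baseline and at least one post-baseline 2MWD, analysed as randomised.
2. State that termination visits remapped under SAP 5.1 count as post-baseline values.
3. Base the information in the conditional-power formula on the MMRM standard error (SE) of the Week 52 difference, or on an equivalent effective n1 = 2s²/SE² with s the standard deviation, and not on the number of subjects included.

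Showing the DMC early dropout by arm would let it judge whether the condition for bias is met. The documents report early termination of the trial but do not say whether the interim took place. If it did, this version can be reported as a sensitivity analysis.

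The cost is a few sentences and slightly more analysis work, with no new data. Subjects with only Week 12 data add little Week 52 information, so the gain is mainly protection against bias, not precision.

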5.3 Sample Size Considerations

The sample size of this clinical study has been calculated based on the primary efficacy endpoint (2MWD) at the end of the treatment period.

Baseline measure of 2MWD in patients with PPS has been estimated in about 120 meters with standard deviation

s between 24 and 28 meters. The standard deviations for change from baseline to week 3 and week 17 in 2MWD are in the range of 8 to 11 meters [Horemans HL, Nollet F, Beelen A, et al., Stolwijk-Swüste JM, Beelen A, Lankhorst GJ, et al., Horemans HL, Beelen A, Nollet F, et al]. In order to show the superiority of Flebogamma® 5% DIF over placebo, an effect size of 5% (6 meters) in change from estimated baseline in 2MWT (120 meters) is assumed.

A clinically relevant change in distance walked at the end of the treatment period (after 52 weeks of treatment) between groups (Flebogamma[®] 5% DIF versus placebo) has been stated to be 5%.

In order to show the treatment difference of 6 meters in 2MWD with a standard deviation of 11 meters, 99 subjects need to be randomised into one of three treatment arms in Stage 1 and 66 subjects need to be randomised into one of two treatment arms in Stage 2. To account for a 20% dropout rate, approximately 126 will be randomised into one of the three treatment arms (42 subject/arm) in Stage 1, and approximately 84 subjects will be randomised into one of the two treatment arms (42 subject/arm) in Stage 2.

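### The conditional-power formula that selects the dose (SAP 5.4) has n1 where n1+n2 is needed and calls s a standard error, so the observed 1 g/kg benefit that rules out 2 g/kg falls from 5.3 m to between 4.1 and 1.1 m

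*SAP*

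**What the plan says.** SAP 5.4 gives the only efficacy criterion for the trial's one adaptation. Under the condition "Given no safety concern for the Flebogamma" doses, 2 g/kg goes forward if the conditional power of the 2 g/kg "arm is at least 10% relatively higher than" that of the 1 g/kg arm. Otherwise 1 g/kg goes forward.

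The formula is printed twice, as a fraction and in simplified form. Both amount to

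CP = Φ( Z·sqrt(n1/n2) − z(1−α)·sqrt(n1/n2) + δ̂·sqrt(n2/(2s²)) ).

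Z, δ̂ and s come from the interim MMRM. The text defines s as follows: "s is the estimated standard error for the mean of treatment". It defines n1 as the number in the interim analysis for the arm, and says "n_2 is the number of subjects planned to be enrolled for treatment arm at Stage 2". It does not define α. Protocol 10.1.4 gives the same 10% rule without a formula and leaves further detail to the DMC charter.

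The final test in SAP 10.1 combines the stages by the inverse normal method with weights sqrt(n1/(n1+n2)) and sqrt(n2/(n1+n2)), and adds a Simes test of the intersection hypothesis.

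**The concern.** Conditional power should be the chance that the final test rejects, given the interim data. The SAP 5.4 formula does not match the SAP 10.1 test.

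- **Critical value.** n2 is the Stage 2 number alone, not a cumulative total, so no reading of n2 restores the missing n1+n2. The fraction and the simplified form agree algebraically, so a fault in reading the PDF is unlikely.
- **Definition of s.** n2/(2s²) is statistical information only if s is the SD of one subject's change. With a standard error in its place, the drift term grows by a factor of sqrt(n1) (SE of an arm mean) or sqrt(n1/2) (SE of the difference).

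Both errors push conditional power upward. Under a relative 10% rule that defaults to 1 g/kg, two inflated values near 1 cannot be separated, so the rule stops responding to the difference between the doses. At stake are which arm goes to Stage 2 and the power of the confirmatory test. SAP 10 also restricts the secondary and exploratory analyses to placebo and the selected dose.

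**Working it through.** **Inputs**
- Per-arm size. SAP 5.3 needs 99 subjects over three arms, or 33 per arm. Allowing 20% dropout, 33/0.8 = 41.25, rounded up to 42. Then 3 × 42 = 126 and 2 × 42 = 84, which reproduces the plan: "approximately 126 will be randomised into one of the three treatment arms (42 subject/arm) in Stage 1", and 84 in Stage 2. So n2 = 42.
- n1: the interim is triggered when at least 80% of Stage 1 have finished treatment. 0.8 × 42 = 33.6, taken as 34 (an assumption).
- SD 11 m, the value used for sample size. SAP 5.3 says the SDs of change "are in the range of 8 to 11 meters", so 8 m is also run.
- α = 0.025 one-sided (Protocol 10.3), z = 1.960. This is the same level as the two-sided 0.05 in SAP 5.

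**Correct term.** For one arm, SAP 10.1 rejects when sqrt(n1/(n1+n2))·Z1 + sqrt(n2/(n1+n2))·Z2 > z. Solving for Z2, the threshold is z·sqrt((n1+n2)/n2) − Z1·sqrt(n1/n2). The current-trend conditional power is therefore

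CP = Φ( Z·sqrt(n1/n2) − z·sqrt((n1+n2)/n2) + δ̂·sqrt(n2/(2·SD²)) ).

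Simulation agrees within 0.001. As a limiting check, with n1 → 0 and δ̂ = 0 this gives α, while the printed formula gives Φ(0) = 50%.

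**Lock-in point.** 2 g/kg is impossible once CP for 1 g/kg exceeds 1/1.1 = 0.909 (normal quantile 1.335). Put d for the observed 1 g/kg difference and Z = d/(SD·sqrt(2/n1)).
- First term: d·34/(11·sqrt(84)) = 0.337d.
- Drift with s = 11: d·sqrt(42/242) = 0.417d.
- Drift with s = 11·sqrt(2/34) = 2.67 (SE of the difference): 1.718d.
- Drift with s = 11/sqrt(34) = 1.89 (SE of an arm mean): 2.429d.
- Critical term: corrected 1.960·sqrt(76/42) = 2.637; printed 1.960·sqrt(34/42) = 1.763.

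| Version | Equation | d (m) |
|---|---|---|
| Corrected | (1.335+2.637)/0.754 | 5.27 |
| Printed, s = SD | (1.335+1.763)/0.754 | 4.11 |
| Printed, s = SE of difference | (1.335+1.763)/2.055 | 1.51 |
| Printed, s = SE of arm mean (literal) | (1.335+1.763)/2.766 | 1.12 |

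In the same order, SD 8 gives 3.8 / 3.0 / 1.1 / 0.8 m, and n1 = 42 gives 4.9 / 4.0 / 1.4 / 1.1 m.

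**Example.** Suppose the observed differences are 2 m (1 g/kg) and 8 m (2 g/kg). The 1 g/kg conditional power is 0.13 / 0.40 / 0.99 / 0.9999, and the 2 g/kg value rounds to 1.00 throughout. The first two versions select 2 g/kg; the last two select 1 g/kg.

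**Simulation.** 1,000,000 trials per scenario, shared placebo arm, SD treated as known. Selection used 34 per arm; the full SAP 10.1 test used 42 per arm in Stage 1 and 42 in Stage 2. Columns follow the table order.

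| True effect, 1 vs 2 g/kg (m) | 2 g/kg selected, % | Power, % |
|---|---|---|
| 0 vs 6 | 96.4 / 92.8 / 71.1 / 66.0 | 87.6 / 84.5 / 64.5 / 59.7 |
| 3 vs 6 | 71.9 / 60.4 / 27.9 / 23.4 | 84.7 / 80.2 / 61.6 / 58.5 |
| 5 vs 6 | 40.4 / 29.1 / 8.7 / 6.8 | 91.7 / 90.5 / 86.1 / 85.5 |
| 6 vs 6 | 25.5 / 16.8 / 4.0 / 3.0 | 95.6 / 95.3 / 94.3 / 94.1 |

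Power for 3 vs 6 m in other layouts:
- SD 8: 96.2 / 92.7 / 79.5 / 77.5%.
- Completers only (27 at interim, 33 and 33 final, planned n2 = 42 in the formula): 75.5 / 70.3 / 53.3 / 50.4%.
- 10% over-running (46 and 42 per arm): 86.0 / 81.7 / 63.5 / 60.5%.
- Extreme under-running, where no one joins Stage 1 after the first 34 per arm and "the remaining subjects not randomized in the Stage 1 will be reallocated to Stage 2": 3 × 8 = 24 move, 12 per arm, giving 34 and 54. Power 85.7 / 81.4 / 63.2 / 60.2%.

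One-sided type I error at 0 vs 0 m is 2.3 / 2.2 / 2.0 / 1.9%.

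**The case against.** The algebra is not in dispute. The case against giving it weight is as follows.

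- **Termination.** SAP 2 and 12.1 report a July 2022 decision to stop once current subjects had finished treatment. SAP version 3.0 is dated 28 August 2023, more than 52 weeks later, so a Stage 2 cohort is unlikely to be left to direct. This largely stands, and it makes a prospective correction the least likely of the three remedies. It does not remove the point, because version 3.0 still carries the formula and still analyses a selected dose.
- **Unknown implementation.** Neither the DMC charter, the program nor the SAP version in force at any interim is available, and the rule also depends on safety. This stands. The 1.1 m figure holds only if the text was programmed literally; with s as the SD, the shift is 5.3 to 4.1 m.
- **Harm depends on the scenario.** The plan assumes a single 6 m effect. At 6 vs 6 m the worst reading costs 95.6 − 94.1 = 1.5 points of power. This stands; large losses need 2 g/kg to be clearly better than 1 g/kg, which the documents do not assume.
- **Some of it is design.** The 0.909 ceiling and the default to 1 g/kg exist under any formula. This too stands; the errors only lower the observed benefit at which the ceiling is reached.

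**Conclusion.** The concern holds, and the text must be fixed. SAP 5.4 contradicts the SAP 10.1 test in its critical-value term, and its definition of s does not fit its own formula. With s read as the SD, the most favourable reading, the printed formula costs 71.9 − 60.4 = 11.5 points in the chance of selecting 2 g/kg and 84.7 − 80.2 = 4.5 points of power at 3 vs 6 m. Read literally, it costs 48.5 and 26.2 points. These figures rest on the assumed SD, interim size and α, but the direction is the same in every variant run.

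The primary test remains valid, since the combination test controls type I error whatever selection rule is used. The damage is to dose selection and efficiency. The missing definition of α is a clarification, not a third error. Nothing here says which dose is right.

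**What to change.** The documents do not say whether the interim was run, so one of three actions applies.

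1. **Not run, selection still to come.** In SAP 5.4, replace the critical-value term with z(1−α)·sqrt((n1+n2)/n2). Define s as the model-based SD of the Week 52 change from the MMRM, and state α = 0.025 one-sided. Note that the formula ignores the Simes step and the subjects who join Stage 1 after the data cut. Both approximations are small: including Simes moves selection at 3 vs 6 m from 71.9 to 71.0%, and counting the 8 later subjects per arm moves the lock-in from 5.3 to 5.1 m. Cost: one term, one definition and one stated α, and the same in the DMC charter if it repeats the formula.
2. **Already run.** Do not replace the rule retrospectively. The unblinded statistician should state which s, α and critical term were programmed and recompute both conditional powers. The CSR should disclose the printed and corrected values and any change in the selected arm. Cost: one recomputation and a short disclosure.
3. **No selection made or planned.** Say so in the SAP and state which arms enter the selected-dose analyses. Cost: two sentences.

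None of these needs patients or new data.
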